### **8.2 STATISTICAL ANALYSES**

The baseline visit will be considered as the last available visit on or before the date of sign of informed consent form for the all-enrolled set and the untreated set (as well as any other subgroups corresponding to this untreated set). For the treated set (as well as any other subgroups corresponding to this treated set), the baseline will be considered as the last available value within 3 weeks prior to or 3 weeks after starting tafamidis.

For the subgroup of patients with off-label use, the baseline will be the last available value prior to receiving the first dose of tafamidis 80/61 mg.

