## 9. RESEARCH METHODS

### 9.1. Study Design

THAOS is a non-interventional, global, multi-center, longitudinal observational survey open to all patients with ATTR amyloidosis, including both inherited and wild-type forms of disease, and participants with TTR gene mutations without disease diagnosis. There is no set number of patients who will be enrolled. The study has been open since 2007 and will continue until Pfizer declares the study complete (currently estimated to be the year 2023), or as long as patients are able to participate, or until they withdraw consent.

THAOS does not involve the administration of an investigational agent or other intervention. Patients will continue to receive their current medications and all other standard care for their disease. It is recommended that patient assessments be conducted at least annually and recorded in the THAOS electronic data record close to the time they are performed.

Treatment with tafamidis or with other disease modifying therapies will be according to the product label with commercially available product or according to protocol-specified requirements if a participant is enrolled in a tafamidis interventional study.

In addition to routine procedures for standard of care, patients will be asked to complete patient outcome questionnaires at least annually; these are optional and do not affect a patient's eligibility to participate in the survey.

The THAOS electronic data record allows for data to be recorded from an eligibility/baseline visit, at return visits, and in the form of status updates if the patient has not visited the site. In addition, THAOS physicians have the option of recording pre-baseline retrospective patient data. Final data entry (the entry of a status update indicating that the patient has been discontinued) will occur when the survey is completed, if the patient dies, or elects to discontinue the survey.

Physicians at survey sites will evaluate patients to determine eligibility. Each patient must review and sign an informed consent document before any data are recorded in the THAOS electronic data record. The date the informed consent form is signed will be documented in the THAOS electronic data record.

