### 9.3.3. Eligibility/Baseline Visit

This visit will be performed to determine a patient’s eligibility. It includes obtaining informed consent, chart review to determine eligibility, and recording results of study assessments as outlined in [Section 9.3.1 Study Assessments](#).

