### **9.3.5. Retrospective Visit**

Any assessments listed in [Section 9.3.1](#) Study Assessments and performed prior to the patient's Eligibility/Baseline visit may be entered into the THAOS electronic data record as retrospective visit data. This data collection is optional.

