The investigator, or a person designated by the investigator, will obtain written informed consent from each patient or the patient's legally acceptable representative before any study-specific activity is performed. The investigator will retain the original of each patient's signed consent/assent document.

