## **11.2. Reporting Period**

For each patient, the safety event reporting period begins at the time of the patient's first dose of tafamidis or the time of the patient's informed consent if s/he is being treated with tafamidis at study start and lasts through the end of the observation period of the study, which must include at least 28 calendar days following the last administration of a drug under study; a report must be submitted to Pfizer Safety (or its designated representative) for any of the types of safety events listed in the table above occurring during this period.

If a patient was administered a drug under study on the last day of the observation period, then the reporting period should be extended for 28 calendar days following the end of observation.

Most often, the date of informed consent is the same as the date of enrollment. In some situations, there may be a lag between the dates of informed consent and enrollment. In these instances, if a patient provides informed consent but is never enrolled in the study (eg, patient changes his/her mind about participation), the reporting period ends on the date of the decision to not enroll the patient.

If the investigator becomes aware of a SAE occurring at any time after completion of the study and s/he considers the SAE to be related to tafamidis, the SAE also must be reported to Pfizer Safety.

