## APPENDIX 2: DATA DERIVATION DETAILS

### A1.1 Definition and use of visit windows in reporting

For All enrolled set and tafamidis untreated set (as well as the subgroups corresponding to untreated set), Day 1 will be the most recent available value collected either on or after the informed consent signed date. The study day will be calculated as follows:

Study day = assessment date – consent date

For the tafamidis treated set (as well as the subgroups corresponding to treated set), Day 1 will be the most recent available value collected either on or after the first dose of tafamidis received after enrollment in THAOS. The study day will be calculated as follows:

Study day = assessment date – date of first dose of tafamidis after enrollment in THAOS / consent date if patient was continuing taking tafamidis prior to enrollment (whichever is earlier) + 1

The following visit window will be applied, considering the absolute value of study day (absday):

Condition	Visit	Year
$\text{absday} < -365.25 \times 0.5$	-1	
$0 \leq \text{absday} \leq 365.25 \times 0.5$	0	
$365.25 \times 0.5 < \text{absday} \leq 365.25 \times 1.5$	1	1
$365.25 \times 1.5 < \text{absday} \leq 365.25 \times 2.5$	2	2
$365.25 \times 2.5 < \text{absday} \leq 365.25 \times 3.5$	3	3
$365.25 \times 3.5 < \text{absday} \leq 365.25 \times 4.5$	4	4
$365.25 \times 4.5 < \text{absday} \leq 365.25 \times 5.5$	5	5
$365.25 \times 5.5 < \text{absday} \leq 365.25 \times 6.5$	6	6
$365.25 \times 6.5 < \text{absday} \leq 365.25 \times 7.5$	7	7
$365.25 \times 7.5 < \text{absday} \leq 365.25 \times 8.5$	8	8
$365.25 \times 8.5 < \text{absday} \leq 365.25 \times 9.5$	9	9
$365.25 \times 9.5 < \text{absday} \leq 365.25 \times 10.5$	10	10
$365.25 \times 10.5 < \text{absday} \leq 365.25 \times 11.5$	11	11
$365.25 \times 11.5 < \text{absday} \leq 365.25 \times 12.5$	12	12

Note: If study day is missing, then visit will be considered as missing.

CCI [REDACTED]

	CCI [REDACTED]	[REDACTED]	[REDACTED] → [REDACTED]
CCI [REDACTED]	[REDACTED]	[REDACTED]	[REDACTED]
[REDACTED]	[REDACTED]	[REDACTED]	0 → 4 1 → 3.75 2 → 3.5 3 → 3.25 4 → 2 5 → 0
[REDACTED]	[REDACTED]	[REDACTED]	Present → [REDACTED] [REDACTED] → [REDACTED]
[REDACTED]	[REDACTED]	[REDACTED]	Normal → [REDACTED] Decreased → [REDACTED] Absent → [REDACTED]
CCI [REDACTED]	[REDACTED]	[REDACTED]	[REDACTED]

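### SAP 8.2 and Appendix 2 anchor the all-enrolled and untreated baseline on opposite sides of consent, so an Eligibility/Baseline visit dated after consent is not used as baseline

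*SAP*

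**What the plan says.** SAP 8.2 defines baseline for the all-enrolled and untreated sets, and their subgroups, by the consent signature: "The baseline visit will be considered as the last available visit on or before the date of sign of informed consent form". No earliest date is given. The treated set, in the same paragraph, is bounded on both sides: "the baseline will be considered as the last available value within 3 weeks prior to or 3 weeks after starting tafamidis".

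SAP Appendix 2 (A1.1) gives another anchor for the all-enrolled and untreated sets: "Day 1 will be the most recent available value collected either on or after the informed consent signed date". Visits are then windowed on the absolute value of study day, with Visit 0 running from 0 to half a year.

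The protocol has its own baseline visit. Section 9.3.3 says of the Eligibility/Baseline visit: "It includes obtaining informed consent, chart review to determine eligibility, and recording results of study assessments". Under 9.3.5, assessments made before that visit "may be entered into the THAOS electronic data record as retrospective visit data. This data collection is optional".

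**The concern.** The protocol collects baseline data at a visit that includes consent. SAP 8.2 selects by date and looks only backwards from the signature. If the Eligibility/Baseline visit carries a date after the signature, 8.2 cannot select it. What remains is whatever retrospective visit the site chose to enter, however old, or nothing.

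Appendix 2 looks forwards from the same date. Two programmers could therefore derive different baselines for one patient, and each could cite the SAP.

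The untreated set supports the natural-history objective. The visible untreated outputs that depend on this baseline are:

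- change in blood pressure by year;
- change in ECG intervals by year, in the cardiac and mixed phenotypes and in patients who move from neurologic to mixed;
- the echocardiogram tables, which are summarised at baseline only.

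**Working it through.** The documents state no figure on this point, so there is none to reproduce. The check applies each rule to assumed visit dates.

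**Rules, in days relative to consent (consent = 0)**

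- SAP 8.2: baseline = the largest visit day d with d ≤ 0.
- Appendix 2, kinder reading: the smallest d with d ≥ 0.
- Appendix 2, literal reading of *most recent*: the largest d with d ≥ 0.
- Visit 0 window: 0 ≤ |d| ≤ 365.25 × 0.5 = 182.625.

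**Results.** All dates are assumptions. Negative days are retrospective visits, the first non-negative day is the Eligibility/Baseline visit, and the last day is a return visit.

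| Visit days | 8.2 baseline | Appendix 2, earliest | Appendix 2, literal |
|---|---|---|---|
| 0, 365 | 0 | 0 | 365 |
| −730, 0, 365 | 0 | 0 | 365 |
| 1, 365 | none | 1 | 365 |
| 30, 365 | none | 30 | 365 |
| −90, 14, 365 | −90 | 14 | 365 |
| −730, 14, 365 | −730 | 14 | 365 |
| −1500, 60, 400 | −1500 | 60 | 400 |

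**Reading the table**

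1. With a visit on the consent date, 8.2 selects it, even when an older retrospective visit exists. Nothing is lost. The kinder reading of Appendix 2 agrees; the literal reading does not once any follow-up exists.
2. With the visit one day late and no retrospective entry, 8.2 selects nothing. Every change from baseline for that patient is then missing.
3. With the visit late and a retrospective entry present, the age of that entry decides how stale the baseline is. At −90 days the harm is modest. At −730, the Year 1 change spans 365 + 730 = 1,095 days (3.0 years) instead of 365 − 14 = 351 days. At −1500, it spans 400 + 1500 = 1,900 days (5.2 years) instead of 400 − 60 = 340 days.
4. The visits at days 1, 14, 30 and 60 all lie within 182.625 days of consent, so Appendix 2 labels them Visit 0 while 8.2 refuses them as baseline.
5. Because windows use absolute days, a baseline at −730 falls between 547.875 and 913.125 and is labelled Visit 2. One at −1500 falls between 1,278.375 and 1,643.625 and is labelled Visit 4. The window row meant for earlier visits requires an absolute value below −182.625, which cannot occur.

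**Forms without a fallback.** SAP Table 2 marks medical history, TTR data and family history at the Eligibility/Baseline visit only. If 8.2 is applied by date to these forms, a patient whose visit is dated after consent has no retrospective substitute.

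**The case against.** The strongest reply is that the ordinary case works. Consent belongs to the Eligibility/Baseline visit, so a same-day visit is on or before consent and, being the last such visit, beats any retrospective one. This stands, and it limits the point to visits dated after consent.

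Protocol 11.2 does say "there may be a lag between the dates of informed consent and enrollment", and a reader might infer that late baselines are common. It does not support that. The sentence just before it says the two dates most often coincide, the section concerns safety reporting for tafamidis-treated patients, and SAP 5.1 equates enrollment with the consent date. The passage shows only that a gap is conceivable.

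A reader might also infer late dates from the worksheets for outside specialists in SAP Table 2. The visible footnote attaches to renal/bladder ultrasound, eye examination and body composition. It is not on the general examination, which holds vital signs, and no ECG row is visible. Further, 8.2 selects a *visit* for these sets but a *value* for the treated set. A later specialist result filed under a consent-dated visit might therefore still count; the SAP does not say.

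Nor do the consent rules force baseline assessments to fall after consent. Protocol 9.1 says "Each patient must review and sign an informed consent document before any data are recorded in the THAOS electronic data record", and 10.2 requires written consent from the patient or the "legally acceptable representative before any study-specific activity is performed". But recording is not performing, and Protocol 9.2 describes the assessments as components of standard clinical practice.

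It can be said, too, that Appendix 2 only labels visits and does not define baseline. Its sentence nevertheless selects a value for Day 1, and even as a labelling rule it puts into Visit 0 a visit that 8.2 will not accept.

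Finally, all analyses are descriptive, untreated survival runs from enrollment rather than from this baseline (SAP 6.2.1), and the efficacy endpoints are redacted. Any effect on redacted progression outputs cannot be judged.

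**Conclusion.** The point holds in limited form. SAP 8.2 and Appendix 2 conflict for the same two sets. When the Eligibility/Baseline visit is dated after consent, 8.2 excludes it in favour of a retrospective visit of unlimited age or of no baseline at all. This follows from the wording and needs no assumption about frequency.

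The number of patients affected is unknown; the protocol suggests that same-day visits are usual. The intervals of 3.0 and 5.2 years shown above are illustrations on assumed dates. A reader might turn them into multiples of disease progression, or conclude that any patient with an old retrospective visit has years of change booked to Year 1. The documents support neither. The first needs linear progression, which is not established for blood pressure or ECG intervals. The second needs a baseline visit dated after consent and no nearer earlier visit.

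The conflict should be resolved before baseline is derived for the final report. It does not put the untreated analyses as a whole in doubt.

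**What to change.** - In SAP 8.2, define baseline for the all-enrolled and untreated sets as the Eligibility/Baseline visit value.
- If that value is missing, use the one nearest to consent within a stated window. The SAP's own half-year Visit 0 limit would serve. For patients who start tafamidis after enrollment, require it to precede the first dose. Do not use values outside the window as baseline.
- State whether visit date or assessment date governs.
- Replace the Day 1 sentence in Appendix 2 with the same rule, and window on signed study day so that retrospective visits cannot receive follow-up labels.

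The cost is one paragraph, one appendix sentence, the window correction and one derivation. Patients with a consent-dated baseline visit are unchanged. The downside is small: a patient with no Eligibility/Baseline value, whose only other value is older than the window, loses a nominal baseline. The half-year width is a choice, and another stated limit would also resolve the conflict.

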### Assessments

A series of assessments will be used to assess disease progression and the effects of tafamidis treatment including demographics, TTR genetic test results, tissue biopsy results, family disease history, medical history, annual medical assessment, general examination, concomitant medication use, hospitalizations, transplant history and complications related to transplantations, AE/SAE reporting for tafamidis-treated patients, health events of interest, clinical laboratory data, urinalysis, CCI [REDACTED], [REDACTED] neurologic assessments, eye examination, body composition, CCI [REDACTED], [REDACTED] and death.

Data will be collected at an eligibility/baseline visit, return visits, and in the form of status updates if the patient has not visited the site. In addition, pre-baseline retrospective data may optionally be captured.

Return visits will be conducted annually (on average) or at the discretion of the survey physician. The reporting window for collecting changes in signs, symptoms, AEs, and new diagnoses is from the last prior visit.

A final visit, including collection of AE/SAE information will be performed at the completion of the survey or at the time the patient elects to discontinue, whichever occurs first. For patients enrolled in interventional clinical trials that include open-label tafamidis or other open label investigational products, follow-up in THAOS may continue, but AE data collection and reporting will be addressed through the interventional clinical trial sponsor. If a patient dies while enrolled in the survey, the site is asked to collect all available information related to the death.

If a patient enrolls in a double blind investigational clinical trial or any other trial (including Tafamidis Compassionate Use/Early Access Program) during the course of their follow-up in THAOS, data collected for such patients (if included in the THAOS database) will be excluded from analyses specified within this SAP.

AE/SAE data collected in THAOS will be used to further characterize the safety profile of tafamidis and as a result, to fulfil certain aspects of the European Union (EU) post-

marking commitment for tafamidis. Based on the safety concerns detailed in Table 1, corresponding data for Health Events of Interest will be summarized to characterize both the natural history of ATTR amyloidosis in participants not treated with tafamidis and safety concerns amongst tafamidis-treated patients.

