## 5.3 TAFAMIDIS TREATED

The tafamidis treated set will include the following:

[figure not shown]
- All available data from the enrollment date until final treatment discontinuation of tafamidis or end of follow-up in THAOS (whichever is earlier) for patients who have been enrolled in THAOS, signed the informed consent and who were on tafamidis treatment on or prior to the date of enrollment in THAOS.
- All available data from first dose of tafamidis until final treatment discontinuation of tafamidis or end of follow-up in THAOS (whichever is earlier) for patients who were not on tafamidis at the time of enrollment in THAOS but subsequently initiated treatment with tafamidis.

Note: A patient can be considered part of both the tafamidis untreated and tafamidis treated sets if the patient initiated treatment with tafamidis after beginning participation in THAOS.

The below schematic will help to better understand the patient population to be analysed:

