## 7 HANDLING OF MISSING VALUES

Missing observations will be treated as missing except for dates. For dates with missing days but not missing months, the 1st of the month will be imputed, and for dates with missing months and days, July will be imputed for months and the 15th will be imputed for days.

For any missing data (CCI [REDACTED]) corresponding to PRO, the PRO specific scoring manual will be utilized for imputation.

Patients with missing data for a variable will be excluded from the denominator when calculating proportions involving observed data for that variable.

If the tafamidis start day is missing, it will be imputed as the 15th of the corresponding month as per the eCRF guidelines. For date of birth, if only year is collected, then the day and month will be considered as 1st of January.

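### The treated-set baseline in SAP 8.2 has no rule for patients already on tafamidis at enrollment and does not match Appendix 2; it also ranks a post-dose value above a pre-dose one

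*SAP*

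**What the plan says.** SAP 8.2 gives one baseline definition for the whole treated set and its subgroups: "the baseline will be considered as the last available value within 3 weeks prior to or 3 weeks after starting tafamidis". It states no order of preference between the two sides of the window and no separate rule for anyone. The off-label subgroup, defined directly afterwards, has a strictly pre-dose baseline: the last value before the first 80/61 mg dose.

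SAP 5.3 builds the treated set from two kinds of patient. Those on tafamidis on or before enrollment contribute "All available data from the enrollment date until final treatment discontinuation of tafamidis". Those who start later contribute "All available data from first dose of tafamidis until final treatment discontinuation of tafamidis".

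Appendix 2 (A1.1) derives study day for the treated set from the first dose after enrollment, or from the "consent date if patient was continuing taking tafamidis prior to enrollment", taking the earlier date and adding 1. It also says that "Day 1 will be the most recent available value collected either on or after the first dose of tafamidis received after enrollment in THAOS".

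Three other provisions matter. Of data from before the baseline visit, Protocol 9.3.5 says "This data collection is optional", and SAP 2.1 agrees. On visit frequency, SAP 2.1 says "Return visits will be conducted annually (on average) or at the discretion of the survey physician". On partial dates, SAP 7 says "If the tafamidis start day is missing, it will be imputed as the 15", meaning the 15th of the known month.

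This baseline feeds the treated-set change-from-baseline summaries in SAP 8.2.6 for hematology and chemistry, blood pressure and ECG intervals.

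**The concern.** The main problem is a gap for patients who enter the registry already on treatment. The 8.2 window sits around the start of tafamidis, which for them may lie months or years before consent, while their treated-set data begin at enrollment. Section 8.2 does not say what to do when the two do not meet. Appendix 2 does recognise these patients and anchors them at consent. One programmer following 8.2 literally would leave the baseline empty or look for retrospective entries. Another, carrying the Appendix 2 anchor across, would use the enrollment visit. The change tables would then differ in who is included and in what change means.

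The second problem is selection order. In a window that runs from 3 weeks before to 3 weeks after first dose, the last value is the post-dose one whenever both sides hold a value. Any early shift in a laboratory value, blood pressure or ECG interval is then absorbed into the baseline.

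**Working it through.** The plan states no figure on this point, so there is nothing to reproduce. The check applies the rule as written.

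**Step 1: patients already on tafamidis.** Put consent at day 0 and the start of tafamidis k days earlier (illustrative values of k). The 8.2 window runs from day −k−21 to day −k+21. Treated-set data begin at day 0 (SAP 5.3). Window days that hold treated-set data = max(0, 22 − k).

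| k (days) | 8.2 window | Days overlapping treated-set data | Consent-visit value usable under literal 8.2 | Appendix 2 study day of consent visit |
|---|---|---|---|---|
| 0 | −21 to +21 | 22 | yes | 1 |
| 7 | −28 to +14 | 15 | yes | 1 |
| 21 | −42 to 0 | 1 | yes | 1 |
| 22 | −43 to −1 | 0 | no | 1 |
| 90 | −111 to −69 | 0 | no | 1 |
| 365 | −386 to −344 | 0 | no | 1 |

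The overlap disappears at k = 22 and stays at zero. Appendix 2 gives the consent visit study day 0 + 1 = 1 throughout and places it in visit 0, which extends to 365.25 × 0.5 = 182.6 days.

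**Step 2: selection order for later initiators.** Put first dose at day 0.

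| Days with a value | 8.2 as written | Pre-dose first |
|---|---|---|
| −7, +14 | +14 | −7 |
| −1, +20 | +20 | −1 |
| +10 in the window, −200 outside it | +10 | +10 |
| −200, +170 | none | none |

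The two readings differ only when the window holds a value on each side.

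**Step 3: how often the order could matter.** Assume fixed visits every T days, a start date unrelated to visits, and a value at every visit. The window has 22 days on or before first dose (−21 to 0) and 21 after it (+1 to +21), 43 in all.

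- T = 30: both sides hold a value in (43 − 30)/30 = 43.3% of starters.
- T = 42: (43 − 42)/42 = 2.4%.
- T of 43 or more: 0%.
- T = 182: post-dose only 21/182 = 11.5%, on or before only 22/182 = 12.1%, none 139/182 = 76.4%.
- T = 365: post-dose only 21/365 = 5.8%, on or before only 22/365 = 6.0%, none 322/365 = 88.2%.

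Starts timed to visits would lower the share with none; skipped assessments would raise it.

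**Step 4: size in a patient whose baseline is post-dose.** If the true change is linear in time, a baseline at day d loses d/t of the change at day t. At day +21 the loss is 21/365.25 = 5.7% at 12 months, and 21/182.6 = 11.5% to 21/547.9 = 3.8% across the Year 1 window. At 12 months, day +14 loses 14/365.25 = 3.8% and day +7 loses 7/365.25 = 1.9%.

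**Step 5: imputed start day.** If the true day is the 1st, imputing the 15th is 14 days late; if it is the 31st, 16 days early. Both dates lie in the same month, so the side of first dose is uncertain only for values dated in that month.

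**The case against.** The strongest reply on the lead point is that the start of tafamidis in 8.2 can be read through Appendix 2, as the first dose after enrollment or consent for continuing users. The enrollment visit then falls in the window and the sections agree. That reading is sensible, but 8.2 neither states it nor refers to Appendix 2, so the need for a sentence remains.

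On selection order, the reply is largely right about size. At fixed intervals of 43 days or more no starter is affected, and the plan expects roughly annual visits. The Year 1 window already pools assessments from about 183 to 548 days, over which a linear change runs from about 50% to 150% of its 12-month value; a 21-day offset is small beside that. Reordering also does nothing for patients with only a post-dose value or none. SAP 8.1 already reports the number of missing values, so part of the proposed count exists, although not split by type of baseline.

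Three stronger readings are not supported. A reader might infer from SAP 5.3 that a pre-dose value cannot serve as baseline for later initiators, because their treated-set data start at first dose; but 8.2 expressly admits values up to 3 weeks before the start. A reader might infer that imputed start days make pre-dose and post-dose values generally indistinguishable; the month is known, the doubt is limited to same-month values when the day is missing, and any rule anchored on the start date inherits it. A reader might also infer a biased comparison or test; SAP 4 states that there are no hypotheses and that everything is descriptive.

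**Conclusion.** The lead point stands. For patients who started tafamidis 22 or more days before consent, 8.2 taken literally yields no baseline from treated-set data, while Appendix 2 anchors them at consent. The documents do not say how many patients this is, so no share can be given. For each one the consequence is either exclusion from the laboratory, blood pressure and ECG change tables or a change measured from a baseline that the SAP does not define. This rests on reading the start of tafamidis as the actual first dose, which is the plain sense.

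The selection-order point stands on the text but is minor. It arises only with two values within 43 days, and a linear effect would lose at most 5.7% at 12 months. Larger losses would need an early-plateau effect, for which the documents give no figure. The frequencies in the check are illustrations under the assumptions stated there, not estimates for this registry.

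The effect is on how the descriptive safety tables read, in a study designated a post-authorization safety study.

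**What to change.** In SAP 8.2:

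- For patients already on tafamidis at enrollment, adopt the Appendix 2 anchor: use the consent-visit value and label it on-treatment.
- For later initiators, keep the 3-week window. Take the last value on or before first dose; only if there is none, take the first post-dose value in the window and flag it.
- Where the start day was imputed, flag a baseline dated in the start month.

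State the same rule in Appendix 2, whose Day 1 wording now admits only values on or after first dose. Report how many treated patients have a pre-dose, post-dose, on-treatment or no baseline.

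The cost is SAP wording and some programming, with no new data. SAP Table 2 shows that tafamidis start and stop dates, and laboratory values and vital signs at the baseline visit, are already on the case report form. The downside is one flag and one extra count. Assessments are recommended rather than required, so some patients will still have no baseline; the count would make that visible.

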### 9.3.4. Return Visit

Return visits will, on average, be conducted annually or more frequently at the discretion of the survey physician. The reporting window for collecting changes in signs, symptoms, AE information, and new diagnoses is from the last prior visit.

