### Hematology and Chemistry

Change from baseline by yearly intervals of the hematology and biochemistry laboratory parameters will be provided using the tafamidis treated set by starting dose.

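### For patients who start tafamidis in THAOS, the 3-week baseline window and the 6-month Visit 0 do not fit together: study days 23 to 182 are neither baseline nor in a yearly interval, and a missing baseline has no fallback

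*SAP*

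**What the plan says.** SAP 8.2 defines the treated-set baseline: "the baseline will be considered as the last available value within 3 weeks prior to or 3 weeks after starting tafamidis". The off-label subgroup has a separate rule: the last value before the first 80/61 mg dose, with no limit on its age.

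SAP Appendix 2 (A1.1) gives the same treated set another anchor: "Day 1 will be the most recent available value collected either on or after the first dose of tafamidis received after enrollment in THAOS". It then assigns visits ("considering the absolute value of study day (absday"). Absolute days from 0 to 365.25 × 0.5 are Visit 0, with the Year cell blank. Year 1 runs from there to 365.25 × 1.5.

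The outputs in SAP 8.2.6 depend on both rules. For laboratory data the plan is "Change from baseline by yearly intervals of the hematology and biochemistry laboratory parameters". Blood pressure follows the same pattern, and ECG is summarised at baseline and by year.

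Three other provisions matter:
- SAP 5.3 starts the treated-set data of a patient who begins tafamidis after enrollment at the first dose.
- SAP 7 leaves missing observations missing, apart from dates.
- Protocol 9.3.4 says "Return visits will, on average, be conducted annually or more frequently", and Protocol 9.3 makes assessments recommended rather than required. I found no assessment tied to the start of tafamidis.

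**The concern.** The baseline rule accepts values up to 3 weeks either side of the start. The first yearly interval opens about 6 months after it. The stretch between has no stated place in the yearly laboratory, blood pressure and ECG tables. Hepatotoxicity is an ongoing important potential risk in SAP Table 1, and the laboratory change tables are the numerical counterpart of the adverse event search, so early on-drug values are of interest.

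The narrow window also decides who is in those tables at all. A starter with no value inside it has no change from baseline in any later year. The patients who remain are those assessed close to the start, and they may not be typical.

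A further effect is easy to miss. If the last available value means the latest in time, a patient with values both before and after the first dose gets the on-drug one as baseline.

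**Working it through.** The documents state no figure for this, so there is nothing to reproduce. The check lays the windows out by day and then asks how often a baseline would be missing.

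**The gap.** A1.1 adds 1 to the treated-set study day, so for a starter the first dose is study day 1.
- Three weeks after the start is 1 + 21 = study day 22.
- Visit 0 ends at 365.25 × 0.5 = 182.625, so its last whole day is study day 182.
- On-drug days in Visit 0 but outside the baseline window are study days 23 to 182: 182 − 22 = 160 days, and 160/365.25 = 43.8%.

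**Absolute days.** Because the sign is dropped, values taken 22 to 183 days before the start (162 days) also fall in Visit 0. A value taken 300 days before the start has study day −299, so it is labelled Year 1. The Visit −1 row requires an absolute value below −182.625 and can never be met.

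**Three rules side by side.** Section 8.2 admits values from 3 weeks before the start. Section 5.3 excludes everything before first dose for these patients. The Day 1 rule admits any value on or after first dose with no 3-week limit. No single derivation satisfies all three.

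**Starters with no baseline.** The window holds 21 + 1 + 21 = 43 days. Let T be the days between visits and q the share of starters whose start falls within 3 weeks of a visit because the two are linked. The remaining starts are taken as unrelated to visits, and every visit is assumed to supply the measurement. Then

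P(no baseline) = (1 − q) × (1 − 43/T).

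| Visit spacing | q | P(no baseline) |
|---|---|---|
| Annual (T = 365.25) | 0 | 1 − 0.118 = 88% |
| Annual | 0.25 | 66% |
| Annual | 0.5 | 44% |
| Annual | 0.75 | 22% |
| Annual | 0.9 | 9% |
| Annual | 1 | 0% |
| 6-monthly (T = 182.6) | 0 | 76% |
| 3-monthly (T = 91.3) | 0 | 53% |

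A continuous-time simulation with q = 0 gave 89%, 77% and 54% for the three spacings. The documents give neither q nor the actual spacing. Because assessments are optional, the share for a single parameter could be higher than shown.

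**Early stoppers.** Someone who stops by study day 182 has no on-drug value in Year 1. The note at the end of SAP 8.2.6 extends safety data to 28 days after the last dose. Since 182.625 − 28 = 154.6, a patient whose last dose is on study day 155 or later could still supply a Year 1 value, but off drug.

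**The case against.** A reader might infer that values in the gap are reported nowhere. The documents do not support that. Visit 0 is a defined category, a blank Year cell does not mean it is suppressed, and the Day 1 rule could be read to admit these values. The closing note of SAP 8.2.6 also names laboratory, vital signs and ECG among the data summarised up to 28 days after the last dose. It sets an end date, however, and gives no interval in which the values would appear. The SAP is thus silent and inconsistent on the gap; it does not plainly exclude these values.

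A reader might also infer that the first half-year on drug is unseen for safety, or that early stoppers contribute no on-drug value. Neither holds. Adverse events, deaths and hospitalizations in the gap are summarised, AEs leading to withdrawal have their own summary, and hepatotoxicity and thyroid change are searched through MedDRA queries. An early stopper can supply an on-drug value in the first 3 weeks, although it counts as baseline.

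Nor can one say that most starters lack a baseline. That needs q to be low, and linking a drug start to a clinic visit is plausible. Visits may also be more frequent than annual.

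Finally, a short window has a purpose. In a progressive disease an old baseline can count pre-treatment worsening as on-treatment change. All analyses are descriptive (SAP 4), and SAP 8.1 shows counts of missing values, so attrition would be visible. This stands against prescribing a particular look-back. It does not justify having no fallback or letting on-drug values displace pre-dose ones. SAP 8.2 already uses an unlimited look-back for the off-label subgroup.

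**Conclusion.** The mismatch stands, for patients who start tafamidis within THAOS and for laboratory, blood pressure and ECG summaries only. Study days 23 to 182, about 44% of the first treatment year, are neither baseline nor in a yearly interval. Patients who stop in that time give no on-drug change from baseline in the yearly tables. These results follow from the text.

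The share of starters with no baseline does not. Under annual visits it runs from 0% to about 88%, depending on how closely starts follow visits, so it should be quoted only as a range. It can be counted from the database before the tables are programmed.

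This should be fixed, because the three rules cannot all be programmed as written and the choice changes who appears in the safety tables. It does not undermine the adverse event analyses.

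**What to change.** 1. Reconcile SAP 5.3, 8.2 and A1.1 into one treated-set baseline for starters: the last value on or before first dose, with a value up to 3 weeks after only as fallback. State a look-back limit and add a sensitivity summary by age of the baseline value. The limit is the sponsor's choice, and 183 days is one option. With the 21-day fallback that gives 183 + 21 = 204 days. Under annual visits the share with no baseline falls from 88% to 1 − 204/365.25 = 44% when q = 0, and from 44% to 22% when q = 0.5.
2. Use signed study days in A1.1, so that pre-dose values do not share windows with on-drug values.
3. Add one treated-set interval, on treatment from the end of the baseline window to day 182, and report laboratory, blood pressure and ECG values and change from baseline in it. Say where a value from the 3-week fallback period goes when a pre-dose value has served as baseline.

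Items 1 and 3 interact. If visits were exactly annual, a patient seen 22 to 181 days after the start was last seen about 343 to 184 days before it (365.25 − 22 and 365.25 − 181), outside a 183-day limit. The new interval should therefore show the values themselves as well as the changes, and this should be weighed when the limit is set.

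The cost is SAP wording and one extra column per table. The downside is that some baselines will be older, which the sensitivity summary would show.
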